9.5.1.5.1 ADVERSE EVENTS AND EVENTS ASSOCIATED WITH SPECIAL SITUATIONS

An AE is any untoward medical occurrence in a patient or clinical investigation subject administered an investigational product. An AE does not necessarily have a causal relationship with the medicinal product. For this study, the study drug is Belviq XR (lorcaserin hydrochloride).

The criteria for identifying AEs in this study are:

- Any unfavorable and unintended sign (including an abnormal laboratory finding), symptom, or disease temporally associated with the use of an investigational product, whether or not considered related to the investigational product (Note: Every sign or

symptom should not be listed as a separate AE if the applicable disease [diagnosis] is being reported as an AE)

- Any new disease or exacerbation of an existing disease
- Any deterioration in non-protocol-required measurements of a laboratory value or other clinical test (eg, ECG, x-ray) that results in symptoms, a change in treatment, or discontinuation of study drug
- Recurrence of an intermittent medical condition (eg, headache) not present pretreatment (Baseline)
- An abnormal laboratory test result should be considered an AE if the identified laboratory abnormality leads to any type of intervention, withdrawal of study drug, or withholding of study drug, whether prescribed in the protocol or not.

All AEs observed during the study will be reported on the Adverse Event CRF. All AEs, regardless of relationship to study drug or procedure, should be collected beginning from the time the subject signs the study ICF through the last visit in the Treatment Phase. Subjects who fail screening primarily due to AE(s) must have the AE(s) leading to screen failure reported on the Screening Disposition CRF. SAEs will be collected for 28 days after the last dose.

Abnormal laboratory values should not be listed as separate AEs if they are considered to be part of the clinical syndrome that is being reported as an AE. It is the responsibility of the investigator to review all laboratory findings in all subjects and determine if they constitute an AE. Medical and scientific judgment should be exercised in deciding whether an isolated laboratory abnormality should be classified as an AE. Any laboratory abnormality considered to constitute an AE should be reported on the Adverse Event CRF.

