9.5.2 Schedule of Procedures/Assessments**9.5.2.1 Schedule of Procedures/Assessments**

[Table 2](#) presents the Schedule of Procedures/Assessments for the study.

Table 2 Schedule of Procedures/Assessments in Study APD356-A001-403 (revised per Amendments 01 and 02)															
Phase:	Prerandomization^a	Randomization													
Period:	Screening	Treatment											Follow-Up		
Visit Number:	1	2 ^a	3	4	5	6	7	8	9	10	11 (EOT)	EOS	US ^b	ED	
Day:	-30 to -1	1													
Weeks^{c,d}:		0	1	5	8	12	20	28	36	44	52	56			
Procedure															
Informed Consent	X														
Demography	X														
Medical History	X														
Prior/concomitant medication assessments	X	X	X	X	X	X	X	X	X	X	X	X	X	X	
AE monitoring	X	X	X	X	X	X	X	X	X	X	X	X	X	X	
Inclusion/exclusion criteria	X	X													
Physical Examination ^e	X	X	X			X		X			X	X	X	X	
Vital signs	X	X	X	X	X	X	X	X	X	X	X	X	X	X	
Height	X	X	X	X	X	X	X	X	X	X	X	X	X	X	
Weight	X	X	X	X	X	X	X	X	X	X	X	X	X	X	
Waist circumference	X	X		X		X		X	X		X	X	X	X	
CDC growth chart	X	X		X		X		X	X		X	X	X	X	
Tanner Staging	X	X						X			X	X	X	X	
Routine clinical laboratory tests	X	X	X	X		X		X			X	X	X	X	
Urinalysis	X	X	X	X		X		X			X	X	X	X	
Urine drug and cotinine test	X														
Fasting plasma glucose, insulin, and HbA1c sampling	X	X				X		X			X			X	
T4 and TSH	X							X			X			X	
Testosterone, Estradiol	X							X			X				

Phase:	Prerandomization ^a	Randomization													
Period:	Screening	Treatment											Follow-Up		
Visit Number:	1	2 ^a	3	4	5	6	7	8	9	10	11 (EOT)	EOS	US ^b	ED	
Day:	-30 to -1	1													
Weeks ^{c,d} :		0	1	5	8	12	20	28	36	44	52	56			
Procedure															
Pregnancy test (urine)	X	X	X	X	X	X	X	X	X	X	X	X		X	
Fasting prolactin	X	X				X		X			X			X	
OC, PICP, and Hydroxy-proline		X						X			X			X	
Fasting lipid panel		X						X			X			X	
Urine NTX		X						X			X			X	
PK/PD blood sampling						X		X	X		X ^f		X ^g	X ^f	
AM serum cortisol		X									X			X	
ECG		X						X			X	X		X	
Echocardiograph	X ^h							X			X			X	
Randomization		X													
IxRS	X	X		X	X	X	X	X	X	X	X				
Study drug dispensing		X		X	X	X	X	X	X	X			X		
Collect study medication				X	X	X	X	X	X	X	X	X	X	X	
Drug accounting and compliance			X	X	X	X	X	X	X	X	X		X	X	
Hand x-ray for bone age		X				X		X			X			X	
C-SSRS	X		X	X	X	X	X	X	X	X	X	X	X	X	
Leiter-3		X		X				X			X	X		X	
PHQ-9		X	X	X	X	X	X	X	X	X	X	X	X	X	
Standardized age-appropriate lifestyle modification counseling ⁱ		X	X	X	X	X	X	X	X	X			X		

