9.5.4.1 Reporting of Serious Adverse Events

All SAEs, regardless of their relationship to study treatment, must be reported on a completed SAE form by email or fax as soon as possible but no later than 1 business day from the date the investigator becomes aware of the event.

SAEs, regardless of causality assessment, must be collected through the through the last visit and for 28 days after the subject's last dose. All SAEs must be followed to resolution or, if resolution is unlikely, to stabilization. Any SAE judged by the investigator to be related to the study treatment or any protocol-required procedure should be reported to the sponsor regardless of the length of time that has passed since study completion.

The detailed contact information for reporting of SAEs is provided in the Investigator Study File.

For urgent safety issues, please ensure all appropriate medical care is administered to the subject and contact the appropriate study team member listed in the Investigator Study File.

It is very important that the SAE report form be filled out as completely as possible at the time of the initial report. This includes the investigator's assessment of causality.

Any follow-up information received on SAEs should be forwarded within 1 business day of its receipt. If the follow-up information changes the investigator's assessment of causality, this should also be noted on the follow-up SAE form.

Preliminary SAE reports should be followed as soon as possible by detailed descriptions including copies of hospital case reports, autopsy reports, and other documents requested by the sponsor.

The investigator must notify his/her IRB/IEC of the occurrence of the SAE, in writing, if required by their institution. A copy of this communication must be forwarded to the sponsor to be filed in the sponsor's Trial Master File.

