9.7.1.8.2 ADVERSE EVENTS

The AE verbatim descriptions (investigator terms from the CRF) will be classified into standardized medical terminology using the Medical Dictionary for Regulatory Activities (MedDRA). Adverse events will be coded to the MedDRA (Version 18.0 or higher) lower level term closest to the verbatim term. The linked MedDRA PT and primary system organ class (SOC) are also captured in the database.

A treatment-emergent AE (TEAE) is defined as an AE that emerges during treatment (up to 28 days after the last dose of study drug), having been absent at pretreatment (Baseline) or

- Reemerges during treatment (up to 28 days after the last dose of study drug), having been present at pretreatment (Baseline) but stopped before treatment, or
- Worsens in severity during treatment relative to the pretreatment state, when the AE is continuous.

Only those AEs that were treatment emergent will be included in summary tables. All AEs, treatment emergent or otherwise, will be presented in subject data listings.

The TEAEs will be summarized by treatment group. The following summaries will be reported for TEAEs:

- Incidence of TEAEs in descending order of frequency
- Incidence of TEAEs by SOC and PT
- Incidence of treatment-related TEAEs by SOC and PT
- Incidence of TEAEs by SOC, PT and maximum severity (mild, moderate, or severe)
- Incidence of treatment-related TEAEs by SOC, PT, and maximum severity (mild, moderate, or severe)
- Incidence of TEAEs by SOC, PT, and relationship to study drug (Yes [related] or No [not related])

A subject will be counted only once within a SOC or PT, if the subject experienced more than 1 TEAE within a specified SOC and PT.

The following summaries will also be presented for the treatment-emergent SAEs.

- Incidence of TEAEs leading to death
- Incidence of treatment-emergent SAE by SOC and PT
- Incidence of treatment-related treatment-emergent SAE by SOC and PT

In addition, subjects with TEAEs leading to discontinuation from study drug and AEs of special interest as described in [Section 9.5.4.3.2](#) will be summarized by MedDRA SOC and PT for each treatment group.

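### The end of non-serious AE collection in Section 9.5.1.5.1 does not match Table 2 or the 28-day TEAE window in Section 9.7.1.8.2

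*Protocol*

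**What the plan says.** All references are to protocol v7.0 (Amendment 02), the latest version shown.

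- **Section 9.5.1.5.1, all AEs.** AEs of any relationship are to be "collected beginning from the time the subject signs the study ICF through the last visit in the Treatment Phase".
- **Section 9.5.1.5.1, serious events.** A separate sentence in the same paragraph adds that "SAEs will be collected for 28 days after the last dose".
- **Section 9.5.4.1.** SAEs are collected to the "last visit and for 28 days after the subject's last dose".
- **Section 9.5.2.1, Table 2.** The row "AE monitoring" is marked at every visit from Screening to Week 52, and also at EOS (Week 56), at unscheduled visits and at early discontinuation (ED).
- **Section 9.7.1.8.2.** A TEAE is an "AE that emerges during treatment (up to 28 days after the last dose of study drug"), with no restriction to serious events. "Only those AEs that were treatment emergent will be included in summary tables".
- **Section 9.1.** There are two phases, Prerandomization and Randomization. The second contains a Treatment Period of at most 52 weeks and a Follow-Up Period running to EOS. Neither phase is called the *Treatment Phase*.

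**The concern.** The safety tables count events over one window, and the instruction to sites collects them over another. Because Section 9.5.1.5.1 gives serious events their own extension, its natural reading is that non-serious events stop earlier. On that reading the last 28 days of a completer's TEAE window contain no non-serious events because nobody was asked to record them. A subject who stopped drug some weeks earlier and kept attending would have the same 28 off-drug days recorded. One TEAE incidence table would then pool subjects with different observation windows.

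About 30 sites would each have to choose between the section text and the schedule, and events not recorded at the time are hard to recover. Safety is a stated secondary objective, and the study is part of a postmarketing requirement. The Week 56 visit includes laboratory tests, ECG, physical examination, PHQ-9, C-SSRS and Leiter-3, all of which can bring new non-serious findings to light.

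**Working it through.** **Inputs**
- Treatment Period: at most 52 weeks (Section 9.1).
- EOT at Week 52, EOS at Week 56, visit window ±7 days (Table 2).
- Post-dose TEAE window: 28 days (Section 9.7.1.8.2).
- Completers take the daily dose at the clinic on the Week 52 visit day (Section 9.5.1.4.1), so the last dose can fall on that day.
- Subjects who stop drug early are followed to study completion (Section 9.1). Those who leave the study have ED procedures (Section 9.5.5), and Table 2 schedules nothing after them.

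**The plan's own figure.** EOS minus EOT = (56 − 52) × 7 = 28 days. This equals the TEAE window, so Table 2 and Section 9.7.1.8.2 agree for completers at nominal visit times. With one of the two visits shifted by 7 days the gap is 21 to 35 days. With both shifted in opposite directions it is 14 to 42 days.

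**Completer's TEAE window.** 52 × 7 + 28 = 364 + 28 = 392 days. The post-dose part is 28/392 = 7.1%.

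**Post-dose days open to non-serious AEs.** For a subject who stops drug at week *s* and stays in the study:
- Section 9.5.1.5.1, with the term read as Treatment Period: min(28, 7 × (52 − *s*)).
- Table 2, with collection to Week 56: min(28, 7 × (56 − *s*)).

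| Last dose (week) | Section 9.5.1.5.1 | Table 2 |
|---|---|---|
| 12 | 28 | 28 |
| 44 | 28 | 28 |
| 48 | 28 | 28 |
| 49 | 21 | 28 |
| 50 | 14 | 28 |
| 51 | 7 | 28 |
| 52 (completer) | 0 | 28 |

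For a subject who leaves the study, collection ends at the ED visit under either reading. The post-dose days depend on when that visit takes place and may be close to 0.

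**SAE wording.** Take a subject who stops at Week 12 and is followed to the end. The SAE sentence in Section 9.5.1.5.1, read alone, ends at Week 12 + 4 = Week 16. Section 9.5.4.1 runs to the last visit, Week 52 or 56, which is 36 to 40 weeks later. If the all-AE sentence in Section 9.5.1.5.1 is taken to cover SAEs to Week 52 as well, the gap to Week 56 is 4 weeks.

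**The case against.** The strongest reply is that the shorter window is only one reading. *Treatment Phase* is undefined, and in superseded version v5.0 Section 9.1.2 was headed as a combined randomization and treatment phase containing both the Treatment Period and the Follow-Up Period. On that reading its last visit is Week 56 and everything agrees. The sentence just before the collection rule says that AEs observed in the study go on the CRF, Section 9.5.1.5.1 also requires AEs to be followed for 28 days after the last dose or to resolution, and Table 2 marks Week 56. This stands as evidence of ambiguity. It does not remove the conflict. The supporting heading is no longer in force, the reading makes the SAE extension redundant for completers, and the 28-day follow-up rule concerns events already recorded, not collection of new ones.

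Four stronger inferences are tempting, and the documents do not support them:

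- *The arms are compared over different windows.* That needs stopping to differ by arm, and no figure for this is given.
- *With 40% dropout, 130 × 0.60 = 78 per arm lose the window and 130 × 0.40 = 52 per arm keep it.* The 40% is the sample-size dropout rate. Nothing says these subjects stop drug yet keep attending. Those who leave at ED may have as little post-dose collection as completers.
- *Mood changes after stopping are lost for completers.* PHQ-9 and C-SSRS are given at Week 56, and investigators must judge whether results are AEs. Suicidal behavior is always serious, and suicidal ideation and euphoria go through SAE reporting even when non-serious (Section 9.5.4.3.2). Capture is partial, not absent.
- *SAEs face a nine-month gap.* That arises only if one sentence of Section 9.5.1.5.1 is read alone. Following Section 9.5.4.1 satisfies both, and SAEs that begin more than 28 days after the last dose do not enter the TEAE tables.

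Safety is also descriptive, with no hypothesis testing (Section 9.7.1.8), so no efficacy result or tested comparison is affected.

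**Conclusion.** The inconsistency is real and is in the current text. Section 9.5.1.5.1, read most naturally, ends non-serious AE collection before the window that Section 9.7.1.8.2 tabulates and before the Week 56 monitoring that Table 2 schedules.

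The size, 0 against 28 post-dose days, rests on three assumptions: sites follow Section 9.5.1.5.1 over Table 2, *Treatment Phase* means Treatment Period, and the completer's last dose is on the Week 52 visit day. The contrast is with subjects who stop by about Week 48 and remain in follow-up, whose number the protocol does not give. If sites follow Table 2, completers and retained stoppers both have 28 nominal days and the difference disappears. The matter is of moderate importance: it concerns completeness of the safety data, and no bias between treatment arms has been shown.

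**What to change.** - In Section 9.5.1.5.1, replace the end point tied to the undefined phase with a collection window for all AEs that covers at least the 28 days after the last dose used in the TEAE definition. For completers this means through the existing EOS visit at Week 56.
- State how far that window can be covered for subjects who leave at ED. Without such a statement the change would still leave their post-dose days open, because Table 2 has no later contact for them.
- Use the same SAE window wording in Sections 9.5.1.5.1 and 9.5.4.1.

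The TEAE definition and the Week 56 entry in Table 2 can stay as they are. The cost is a short amendment, matching CRF completion guidance, and slightly more AE recording at a visit that already takes place. Any added contact after ED would be a small further burden.

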Abnormal ECG (corrected QT interval [QTc]) results, if not otherwise considered part of a clinical symptom that is being reported as an AE, should be considered an AE if the QTc interval is greater than 450 msec and there is an increase of more than 60 msec from baseline. Any ECG abnormality that the investigator considers as an AE should be reported as such.

It is the responsibility of the investigator to review the results of the Leiter-3, C-SSRS, and PHQ-9 for all subjects and determine if any result constitutes an AE. Medical and scientific judgment should be exercised in deciding whether an isolated suicidality rating scale response should be classified as an AE (see [Section 9.5.1.5.10](#) for a description of the C-SSRS). (revised per Amendment 01)

All AEs must be followed for 28 days after the subject's last dose or until resolution, whichever comes first. All SAEs must be followed to resolution or, if resolution is unlikely, to stabilization.

Every effort must be made by the investigator to categorize each AE according to its severity and its relationship to the study treatment.

Assessing Severity of Adverse Events

Adverse events will be graded on a 3-point scale (mild, moderate, severe) and reported in the detail indicated on the CRF. The definitions are as follows:

Mild Discomfort noticed, but no disruption of normal daily activity

Moderate Discomfort sufficient to reduce or affect normal daily activity

Severe Incapacitating, with inability to work or to perform normal daily activity

The criteria for assessing severity are different than those used for seriousness (see Section 9.5.1.5.2 for the definition of an SAE).

Assessing Relationship to Study Treatment

Items to be considered when assessing the relationship of an AE to the study treatment are:

- Temporal relationship of the onset of the event to the initiation of the study treatment
- The course of the event, especially the effect of discontinuation of study treatment or reintroduction of study treatment, as applicable
- Whether the event is known to be associated with the study treatment or with other similar treatments
- The presence of risk factors in the study subject known to increase the occurrence of the event
- The presence of nonstudy, treatment-related factors that are known to be associated with the occurrence of the event

Classification of Causality

The relationship of each AE to the study drug will be recorded on the CRF in response to the following question:

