9.5.5 Completion/Discontinuation of Subjects

The investigator may withdraw the subject from the study at any time for safety or administrative reasons. A subject may elect to discontinue the study at any time for any reason. All subjects will continue in the study until the 52-week evaluation is completed. Subjects who discontinue treatment prematurely will be followed up until study completion. All subjects who discontinue the study are to complete the study's early discontinuation procedures indicated in the Schedule of Procedures/Assessments [Table 2](#)).

The investigator will promptly explain to the subject involved that the study will be discontinued for that subject and provide appropriate medical treatment and other necessary measures for the subject. A subject who has ceased to return for visits will be followed up by mail, phone, or other means to gather information such as the reason for failure to return, the status of treatment compliance, the presence or absence of AEs, and clinical courses of signs and symptoms.

Subjects who discontinue early from the study will be discontinued for 1 of these primary reasons: AE(s), lost to follow-up, subject choice, withdrawal of consent, pregnancy, study terminated by sponsor, or other. In addition to the primary reason, the subject may indicate 1 or more of secondary reasons for discontinuation. Study disposition information will be collected on the Subject Disposition CRF.

Detailed retention strategies will be developed and included in study manual. These include a highly trained and competent staff, easy access to the clinic, reminder and follow-up calls, interactive group sessions with games and hands-on nutrition and physical activity demonstrations, random raffle drawings, social events, birthday and holiday cards, and newsletters. In addition, home visits for assessments of families will be an option, as needed, to maximize data collection. This detailed retention plan will help prevent missing data.

A subject removed from the study for any reason may not be replaced.

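### For subjects who stop drug but stay in the study, two sections end SAE collection at different times, and the AE tables leave out events that start more than 28 days after last dose

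*Protocol*

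**What the plan says.** All references are to the current protocol text (version 7.0).

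- Section 9.5.5 keeps subjects in the study after they stop drug: "Subjects who discontinue treatment prematurely will be followed up until study completion".
- Section 9.5.1.5.1 gives the SAE window in one sentence: "SAEs will be collected for 28 days after the last dose". Just before it, the same section says that all AEs "should be collected beginning from the time the subject signs the study ICF through the last visit in the Treatment Phase". It later adds: "All AEs must be followed for 28 days after the subject's last dose or until resolution, whichever comes first".
- Section 9.5.4.1 gives a longer SAE window: "SAEs, regardless of causality assessment, must be collected through the through the last visit and for 28 days after the subject's last dose". It also has SAEs judged related reported with no time limit.
- Section 9.7.1.8.2 defines a treatment-emergent event as one arising up to 28 days past the last dose, and fixes the tabulation rule: "Only those AEs that were treatment emergent will be included in summary tables". All other AEs go to subject listings.
- Section 9.7.1.8.6 has separate by-arm summaries. FDA-defined valvulopathy and pulmonary hypertension are summarised at Weeks 28 and 52, and C-SSRS and PHQ-9 at each scheduled visit. It states no limit by time since last dose.

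**The concern.** There are two problems, and they need separate remedies.

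The first is collection. For a subject who takes drug to Week 52, last dose plus 28 days is Week 56, the end-of-study visit, so the two SAE rules agree. For a subject who stops early and keeps attending, they differ by months. A site that follows only the SAE sentence in 9.5.1.5.1 may stop recording new SAEs while a site that follows 9.5.4.1 continues. No analysis can recover an SAE that was never recorded.

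The second is tabulation, and it remains even if every site follows the longer rule. A death, malignancy, psychosis or case of priapism that starts six weeks after the last dose enters no by-arm AE table. The primary efficacy analysis in 9.7.1.6, by contrast, uses BMI values retrieved after treatment discontinuation. Benefit would be compared over the full year, while adverse events would be compared over time on drug plus 28 days. If the arms stop drug at different rates, the tabulated incidences rest on different observation times per arm.

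**Working it through.** The protocol states no figure for this gap, so there is none to reproduce. The check compares the texts and then measures the follow-up affected.

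**1. When SAE collection ends for a subject off drug but still attending**

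| Source | Stated end |
|---|---|
| 9.5.1.5.1, SAE sentence | last dose + 28 days |
| 9.5.1.5.1, all-AE sentence | last visit in the Treatment Phase |
| 9.5.4.1 | through the last visit and for last dose + 28 days |
| Table 2 | AE monitoring marked at every visit, including Week 56 |

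Sections 9.1 and 9.1.2 define a Prerandomization Phase and a Randomization Phase, the latter split into a Treatment Period and a Follow-Up Period. There is no Treatment Phase. For someone off drug it could end at the last visit on drug or at the Week 52 visit. The all-AE sentence therefore cannot resolve the conflict.

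**2. Follow-up outside the 28-day window, per subject**

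With last dose at week *s*, the window closes at week *s* + 4. Weeks outside it are max(0, 52 − (*s* + 4)) to the Week 52 visit and max(0, 56 − (*s* + 4)) to the Week 56 visit.

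| Last dose | To Week 52 | To Week 56 |
|---|---|---|
| Week 12 | 36 | 40 |
| Week 20 | 28 | 32 |
| Week 28 | 20 | 24 |
| Week 44 | 4 | 8 |
| Week 52 (completer) | 0 | 0 |

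**3. Echocardiography**

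Table 2 schedules echocardiograms at Screening, Week 28, Week 52 and early discontinuation. Table 3 defines early discontinuation as leaving the study, and 9.5.5 requires those procedures of subjects who leave the study. A subject who only stops drug, say at Week 29, next has a scheduled echocardiogram 52 − 29 = 23 weeks later. The 28-day window closes at Week 33, 52 − 33 = 19 weeks before it. A valve lesion first recorded then would miss the treatment-emergent AE table. If it met the FDA definition, it would still count in the Week 52 summary under 9.7.1.8.6.

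**4. Possible total, under assumptions not in the documents**

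Assume stopping times uniform over 52 weeks and every stopper retained to the end.

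- Mean gap to Week 52: 48² / (2 × 52) = 22.15 weeks. Mean gap to Week 56: 52 / 2 = 26 weeks.
- If 10% of 260 stop and stay (26 subjects): 26 × 22.15 = 576 person-weeks to Week 52, or 26 × 26 = 676 to Week 56.
- If 40% do (104 subjects): 2,304 or 2,704 person-weeks.
- Planned follow-up is 260 × 52 = 13,520 or 260 × 56 = 14,560 person-weeks. The share is 4% to 17% to Week 52, or 5% to 19% to Week 56.

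The 40% case is an upper bound. It borrows the dropout rate in 9.7.2, which does not say whether dropout means leaving drug or leaving the study.

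**The case against.** The strongest reply on collection is that the SAE sentence in 9.5.1.5.1 extends the AE window and does not cut it short. SAEs are AEs, the section has AEs observed during the study reported, and 28 days after a Week 52 last dose reaches exactly Week 56. On that reading a subject off drug has everything collected to Week 52, and the two sections differ only over Weeks 52 to 56. This is plausible and may well be what was meant. It depends, however, on reading the undefined Treatment Phase as ending at Week 52 for someone off drug, and the SAE sentence does not present itself as an addition. The ambiguity stands.

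On tabulation, last dose plus 28 days is a common convention, and the protocol leaves further detail to an SAP that is not shown here. A whole-study SAE table may be planned there, and its absence from the protocol would not by itself be an error. But the restriction of summary tables to treatment-emergent events is written into the protocol as a fixed rule, so it is fair to raise it here. An SAP also cannot supply events that a site did not collect.

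A reader might go further and infer that off-drug SAEs and events of interest are lost, or that late valve disease or suicidality would appear only in a listing. The documents do not support this. Section 9.5.4.1 requires collection through the last visit, Table 2 has AE monitoring at every visit, related SAEs are reportable without time limit, and all AEs are listed. Section 9.7.1.8.6 summarises echocardiographic and C-SSRS findings by arm with no 28-day limit. Events such as malignancy, psychosis and priapism have no comparable visit-based summary, and the unlimited reporting rule covers only SAEs judged related.

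**Conclusion.** The point holds in two limited parts. First, the SAE window is stated inconsistently for subjects who stop drug and stay, and the all-AE window does not resolve it, so sites could work to different end dates. Second, under 9.7.1.8.2 deaths, SAEs and study-specific events that start more than 28 days after last dose are listed but not compared by arm in any AE table.

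For one subject the size is plain arithmetic: stopping at Week 20 leaves 32 weeks to Week 56 outside the window. For the trial it is unknown. The 4% to 19% of planned follow-up above is illustrative, and it is time outside the treatment-emergent tables, not time known to be uncollected. The documents give neither stopping rates by arm nor reasons for stopping. It would go too far to say that the tables will understate risk in the active arm, or that those who stop are the subjects most at risk. The protocol should be changed, but the primary efficacy analysis is not affected.

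**What to change.** - Reconcile 9.5.1.5.1 with 9.5.4.1 so that SAEs and the study-specific events of 9.5.4.3.2 share one collection window: the later of the last study visit and 28 days past the last dose.
- In 9.5.1.5.1, replace Treatment Phase with a defined end point that applies to subjects off drug, and check the AE follow-up sentence against it.
- In 9.7.1.8.2, add a by-arm table of deaths, SAEs and 9.5.4.3.2 events over the whole study, whatever the time since last dose. Present it beside the treatment-emergent tables and amend the sentence that restricts summary tables accordingly.

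The cost is a few sentences and one or two extra tables, with no added visits or procedures. The drawback is that whole-study rates include time off drug and may dilute drug-attributable differences, which is why the new table should accompany the treatment-emergent tables and not replace them.
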